10.1 Definitions

The following definitions will be used in the assessment of safety:

Adverse Event (AE) is any untoward or unfavorable medical occurrence in a human subject, including any abnormal sign (for example, abnormal physical exam or laboratory finding), symptom, or disease, temporally associated with the subject's participation in the research, whether or not considered related to the subject's participation in the research.

Serious Adverse Event (SAE) is any adverse event that

- (1) results in death;
- (2) is life-threatening;
- (3) results in inpatient hospitalization or prolongation of existing hospitalization;
- (4) results in a persistent or significant disability/incapacity;
- (5) results in a congenital anomaly/birth defect; or
- (6) based upon appropriate medical judgment, may jeopardize the subject's health and may require medical or surgical intervention to prevent one of the other outcomes listed in this definition (examples of such events include allergic bronchospasm requiring intensive treatment in the emergency room or at home, blood dyscrasias or convulsions that do not result in inpatient hospitalization, or the development of drug dependency or drug abuse).

Life-threatening means that the event places the subject at immediate risk of death from the event as it occurred.

Unanticipated Problem is defined as an event, experience or outcome that meets **all three** of the following criteria:

- is unexpected; AND
- is related or possibly related to participation in the research; AND
- suggests that the research places subjects or others at a greater risk of harm (including physical, psychological, economic, or social harm) than was previously known or recognized.

Possibly related means there is a reasonable possibility that the incident, experience, or outcome may have been caused by the procedures involved in the research

Unexpected means the nature, severity, or frequency of the event is not consistent with either:

- the known or foreseeable risk of adverse events associated with the procedures involved in the research that are described in (a) the protocol-related documents, such as the IRB-approved research protocol, any applicable investigator brochure, and the current IRB-approved informed consent document, and (b) other relevant sources of information, such as product labeling and package inserts; or
- the expected natural progression of any underlying disease, disorder, or condition of the subject(s) experiencing the adverse event and the subject's predisposing risk factor profile for the adverse event.

10.2 Safety Review

Risks will be monitored as follows:

The study staff will ask participants about potential adverse events at each study visit and at the telephone calls at 3 weeks into each treatment period. Participants will be given contact information to report any changes in their medical status or concerns related to study procedures. All AE's will be recorded in REDcap and reviewed by the investigators. If the study team finds out about any SAE, they will document the date that the information was obtained and inform the PI within 24 hours. The PI will review any potential SAE and classify as described above in 10.1 and report as described in 10.3 and will determine follow-up with the subject including potential withdrawal from the study.

Adverse Events (AE) definition are described in section 10.1. The principal investigator in this study, who is a physician, would evaluate rather the AE are expected given the participant illness or they are due to study intervention. All AE will be reported as described below.

The study team and investigators will review all AE on a 4 month basis to determine whether the pattern of adverse events, in total, does not suggest that the research places subjects or others at a greater risk of harm than was previously known. The quarterly reviews will be documented.

10.3 Reporting Plans

The principal investigator at Boston Medical Center/Boston University Medical Campus will report Unanticipated Problems, and Adverse Events to the Boston Medical Center/Boston University Medical Campus IRB in accordance with IRB policies:

- Unanticipated Problems occurring at Boston Medical Center/Boston University Medical Campus will be reported to the IRB within 7 days of the investigator learning of the event.
- Adverse Events (including Serious Adverse Events) will be reported in summary at the time of continuing review, along with a statement that the pattern of adverse events, in total, does not suggest that the research places subjects or others at a greater risk of harm than was previously known.

10.4 Stopping Rules

The study has no stopping rules.

11 Data Handling and Record Keeping

11.1 Source Documents

Source data in the study will consist of vascular images, laboratory results and microscope images. We have standard operating protocols in our Research Unit that meets the “ALCOA” standards: Attributable, Legible, Contemporaneous, Original and Accurate.

Data will be entered directly into REDCap in CRFs designed by BEDAC. Laboratory values will be entered into the master data set by the data management team at BEDAC. BEDAC has uniform policies describing source documents, how to make corrections, and who can access them.

11.2 Case Report Forms

We have contracted with BEDAC to create case report forms using REDCap using established data validation methodology. Primary data entry will be directly into the REDCap instruments. For selected instruments that are used during the vascular health testing, there will be paper forms available to the research assistant performing the study that will be entered into REDCap at a later time. BEDAC has uniform policies for quality assurance at the data entry level and for data quality monitoring.

11.3 Case Report Forms

We have contracted with BEDAC to create case report forms using REDCap using established data validation methodology. Primary data entry will be directly into the REDCap instruments. For selected instruments that are used during the vascular health testing, there will be paper forms available to the research assistant performing the study that will be entered into REDCap at a later time. BEDAC has uniform policies for quality assurance at the data entry level and for data quality monitoring.

11.4 Study Records Retention

Study records will be retained for at least seven years after completion of the study. Documentation of informed consent of subjects will be retained for at least seven years after the study is closed. Such records will be preserved in hardcopy, electronic or other media form and will be accessible for inspection and copying by authorized individuals.

12 Statistical Plan

The overall study design is an AB/BA two-treatment, two-period cross-over trial.

12.1 Study Hypotheses

We hypothesize that treatment with the SGLT2 inhibitor dapagliflozin will have favorable effects on EC function and vascular health in patients with T2DM.

Primary outcome: Treatment with dapagliflozin (SGLT2 inhibitor) will improve EC insulin-signaling in patients with T2DM.

- *Null hypothesis:* There is no effect of dapagliflozin on EC insulin-signaling.
- *Alternative hypothesis:* EC insulin-signaling is changed by dapagliflozin.

Secondary outcome: Treatment with dapagliflozin (SGLT2 inhibitor) will improve endothelial function as measured by flow-mediated dilation in patients with T2DM.

- *Null hypothesis:* There is no effect of dapagliflozin on flow-mediated dilation.
- *Alternative hypothesis:* Flow-mediated dilation is changed by dapagliflozin.

Additional endpoints will include additional measures of additional measures of vascular function and endothelial cell health and circulating biomarkers of endothelial health.

12.2 Sample Size Determination

The primary analysis for this randomized cross-over study will be comparison of the primary endpoint, EC insulin-signaling, and the secondary outcome, flow-mediated dilation, during the dapagliflozin treatment period compared to the placebo treatment period. These continuous outcomes were used to power the study.

In our prior work, we have reported that patients with T2DM have an EC insulin response of $-10 \pm 9\%$ and a flow-mediated dilation response of $6.5 \pm 4.3\%$. These measures are expected to be similar in patients enrolled in the present study. An effect size of (how much) was used to calculate the expected sample size for the study.

The analysis will use a an analysis of repeated measures using Proc Mixed in SAS with conventional REML analysis to compare baseline and follow-up results for each treatment group with an overall significance level two-sided alpha=0.025 given the planned primary and secondary endpoints. In order to ensure 90% power to detect an effect size of 0.25 for each outcome, the study needs to

have at least 35 participants who complete the study (SD of differences, $\sigma=5.8\%$ for EC insulin-signaling and 3.5% for flow-mediated dilation). We estimate that 85% of consented participants (50) will be randomized (42). We estimate that 7% of participants will not complete and 83% will complete (35). The sample size has been calculated using NQuery Advisor [version 8.7.2.0, Statistical Solutions, San Diego, CA].

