4.2.2 Secondary Outcome Measures

Key Secondary Outcome: Flow-mediated dilation of the brachial artery measured by ultrasound. We measure the percentage change in the diameter of the brachial artery before and after a 5 minute cuff occlusion on the arm as a measure of endothelial function. We will measure before and after each treatment period.

Other secondary Endpoints:

- Arterial stiffness measured by tonometry
- Microvascular dilator function by EndoPAT
- Plasma measures of noncoding RNA
- EC measures of noncoding RNA
- EC measures of coding RNA
- Circulating biomarkers of vascular health including BNP and CRP
- Fasting glucose, insulin, and lipid profile
- Body weight and waist circumference

5 Study Design

5.1 Overall design:

The overall design is a single center randomized, double-blind, cross-over, placebo-controlled study of dapagliflozin (an SGLT2 inhibitor) compared to placebo in patients with T2DM. Each treatment period lasts 6 weeks with a 2 week washout period between study treatments. The study intervention is 10mg per day of dapagliflozin compared to placebo. Vascular health measures including EC, vasodilator function, and circulating biomarkers will be measured before and after each treatment period. An outline of the study visits and procedures is in the appendix. A cross-over design is being used in order to be able to be able to minimize variability by comparing within individual effects. Prior studies from our group and others have not shown carry-over effects with regards to the primary outcome measures.

Subjects will be randomized 1:1 ratio to receive SGLT2 inhibitor (dapagliflozin 10mg/day) and then placebo or vice versa. Treatment order will be block randomized in block sizes of 2 or 4. 50 subjects will be consented with the goal of randomizing 42 and having 35 study completers.

Participants will be adult men and women who are outpatients with established T2DM. All participants will receive both study interventions.

The study intervention is an FDA-approved medication used in the FDA-approved study population with the objective of identifying mechanisms of cardiovascular health effects thus the study does not fit into an FDA defined trial Phase.

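### The 0.025 level is unclear: if it is each endpoint's share of a family-wise 0.05, the Holm procedure would be a cheap improvement on a valid fixed split

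*Combined protocol and SAP*

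**What the plan says.** The only statement on the significance level is in section 12.2 (Sample Size Determination): "overall significance level two-sided alpha=0.025 given the planned primary and secondary endpoints". The same section describes the primary analysis as "comparison of the primary endpoint, EC insulin-signaling, and the secondary outcome, flow-mediated dilation", and justifies the sample size with "In order to ensure 90% power to detect an effect size of 0.25 for each outcome", which it says needs 35 completers.

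The two outcomes are ranked. Section 4.2.2 has "Key Secondary Outcome: Flow-mediated dilation of the brachial artery measured by ultrasound", and section 12.1 gives FMD its own hypothesis: "Secondary outcome: Treatment with dapagliflozin (SGLT2 inhibitor) will improve endothelial function as measured by flow-mediated dilation in patients with T2DM".

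No section states a family-wise level of 0.05, names a multiplicity procedure, or gives a testing order. Section 12.3 (Statistical Methods) describes the mixed model but no rule for combining the two tests.

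**The concern.** Two things stand out.

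- **The label.** Tying 0.025 to the presence of two endpoints, and claiming 90% power for each, suggests that 0.025 is one of two equal shares of 0.05. The word *overall* says instead that 0.025 is the total. Two analysts could test each endpoint at 0.025 or, with an even split of 0.025, at 0.0125.
- **The rule.** If the plan is an even split, each endpoint is held to 0.025 even after the other has succeeded. The Holm step-down rule tests the smaller p-value against 0.025 and, if that is significant, the other against 0.05. It has the same family-wise bound and never rejects less.

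At stake are a few points of power per endpoint, rather more for success on both endpoints, and an unambiguous decision rule before unblinding.

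**Working it through.** **Inputs from section 12.2.** Two outcomes; two-sided 0.025; 90% power for each; 35 completers; SD of differences 5.8% (EC insulin-signaling) and 3.5% (FMD).

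**Assumed.** Family-wise alpha 0.05, inferred as above. Correlation between the endpoints is not given, so 0, 0.3 and 0.5 were used. Test: t with 35 − 2 = 33 df and noncentrality d × √35, where d is the treatment difference divided by the SD of differences.

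**The plan's own figure.** An effect size of 0.25 on the SD of differences does not give 35. The normal formula is n = ((2.241 + 1.282)/0.25)² = 198.6, so 199 (202 with the t distribution), and 35 completers give 20.7% power. The standardiser is not defined, and another sentence still holds a placeholder: "An effect size of (how much) was used to calculate the expected sample size for the study". The comparison below therefore starts from the stated target. The d that gives 90% power at 0.025 with 35 completers is 0.62, or 0.62 × 5.8 = 3.6 points for EC insulin-signaling and 0.62 × 3.5 = 2.2 points for FMD.

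**Independent endpoints, by formula.** At d = 0.62 (unrounded 0.6194), power is p₁ = 0.900 at level 0.025 and p₂ = 0.945 (0.9448) at level 0.05.

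- Split, both endpoints: p₁² = 0.810.
- Holm, per endpoint: p₁ + (p₂ − p₁)p₁ = 0.900 + 0.0448 × 0.900 = 0.940.
- Holm, both endpoints: p₁² + 2p₁(p₂ − p₁) = 0.810 + 2 × 0.900 × 0.0448 = 0.891.
- At least one, either rule: 1 − (1 − p₁)² = 0.990. It is the same because Holm's first step is the split's test.

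**Correlated endpoints, by simulation** (1,000,000 pairs of t statistics per case; ranges cover correlation 0 to 0.5):

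| True effects | Quantity | Fixed split | Holm |
|---|---|---|---|
| d = 0.62 on both | Per endpoint | 90% | 93-94% |
| d = 0.62 on both | Both endpoints | 81-83% | 89-90% |
| d = 0.5 on both | Per endpoint | 73% | 78-79% |
| d = 0.5 on both | Both endpoints | 53-59% | 66-70% |
| d = 0.25 on both | Per endpoint | 20.7% | 22.6-23.4% |
| Primary 0.62, FMD none | Primary power | 90.0-90.1% | 90.1-90.2% |
| Primary 0.62, FMD none | FMD false positive | 2.5% | 4.5-4.7% |
| None on either | Any false positive | 4.7-5.0% | 4.7-5.0% |

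**If 0.025 is literally the family-wise level.** An even split tests each endpoint at 0.0125 and gives 84% power at d = 0.62. Holm starts at 0.0125 and gives 88-89%. Neither reaches the 90% claimed for each outcome.

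**Fixed sequence at 0.05 (primary, then FMD), d = 0.62 on both.** Primary 94.5%. FMD 0.945² = 89% if independent, and 89-90% over the correlations used.

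**The case against.** A reader might infer that the plan contains an error, or that it wastes power on both endpoints. The documents do not support either.

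- The even split is an inference, because section 12.2 never writes it out. If it is meant, it controls family-wise error at 0.05, and the trial was nominally sized for it, so nothing is lost against the stated 90% target. This stands, and it makes the point an improvement only.
- The gain needs both effects to be real. With FMD null, primary power barely moves, and the chance of at least one success never changes. This stands.
- Holm is not free of cost. Once one endpoint is significant, the other can be falsely rejected at up to 0.05 instead of 0.025. This stays within the family-wise bound but is a real trade.
- Holm ignores the ranking of primary over key secondary. A fixed sequence respects it and gives the primary the full 0.05 whatever FMD shows. It also gives up FMD if the primary fails, which the apparent equal split does not. It is a legitimate alternative, and the choice depends on whether FMD should be claimable on its own.

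What survives is that the level is ambiguously labelled, no procedure is stated, and on the natural reading a rule exists that never rejects less under the same family-wise bound.

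**Conclusion.** This is a cheap improvement. That Holm never rejects less than the split and keeps the family-wise bound is a mathematical property and needs no effect-size assumption. The size of the gain does need one. With 35 completers and equal real effects at d = 0.62, it is 3-4 points per endpoint and about 7-8 points for both. It is larger at d = 0.5 and close to nil for an endpoint whose partner has no effect. These figures rest on an inferred family-wise 0.05, assumed correlations of 0 to 0.5, and a d back-calculated from the 90% target because the plan's own effect size is undefined.

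A reader might also infer from the word *overall* that family-wise error is uncontrolled. That does not follow. Testing each endpoint at 0.025 bounds the error at 0.05 for this pair, and an even split of a literal 0.025 bounds it at 0.025. What is missing is a statement of which is intended.

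**What to change.** In section 12.2, and repeated in section 12.3, state that the family-wise two-sided alpha is 0.05 across EC insulin-signaling and FMD, controlled by the Holm procedure: the smaller p-value is compared with 0.025 and, if significant, the other with 0.05. Remove *overall* from 0.025. The sample size basis of 0.025 per endpoint can stay, as a conservative one.

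If the sponsor prefers to follow the primary/key-secondary order, state a fixed sequence at 0.05 instead and accept that FMD cannot be claimed if the primary fails. If a family-wise 0.025 is really intended, say so, start Holm at 0.0125, and restate the power for each outcome.

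The cost is one sentence before unblinding, with no change to recruitment or conduct. The downsides of Holm are confidence intervals that are less simple to present and the higher individual false-positive rate (up to 0.05) for a null endpoint whose partner is significant.

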12.3 Statistical Methods

We will compare baseline and follow-up results for each treatment group using analysis of repeated measures with Proc Mixed in SAS. The measures of endothelial phenotype (EC insulin-signaling) and vascular function (flow-mediated dilation) will be our dependent variables and treatment, period, and sequence will be the main independent measures. That is the variables are denoted as y_{ijk} is the observation for the i^{th} sequence ($i=1,2$) j^{th} subject ($j=1,2,\dots,n$) k^{th} period ($k=1,2$).

The model can be described by:

$$y_{ijkl} = \beta_0 + \beta_1 X_{treat} + \beta_2 X_{period} + \beta_{12} X_{treat} X_{period} + s_{ij} + \varepsilon_{ijk}$$

s_{ij} is a random subject effect term and is assumed to be independently and identically distributed with $N(0, \sigma_s^2)$

ε_{ijk} is an error term and is assumed to be independently and identically distributed with $N(0, \sigma^2)$

Two dummy variables are introduced as:

$X_{treat} = 1$ if the subject is in treatment B, and $X_{treat} = 0$ otherwise;

$X_{period} = 1$ if the subject is in period 2, and $X_{period} = 0$ otherwise;

Model fitting and inference will follow conventional REML analysis in the Proc Mixed procedure in SAS. The between-subject variation includes a carry-over treatment effect and between-subject residuals. The within-subject variation includes direct treatment effect, period effect, and within-subject residuals. A significant period effect reflects evidence of carry-over effect. A significant within-subject treatment effect is consistent with differences between the two treatments adjusting for carry-over and period effect. In exploratory analyses, we will evaluate for effect modification by sex and race. We will evaluate additional exploratory outcomes in a similar fashion.

Analysis Datasets: The intention-to-treat (ITT) analysis dataset will be the source of data for primary analyses. This will include all randomized participants regardless of actual receipt or compliance with therapy. The per protocol analysis will be conducted based on adherence to assigned treatment (defined as more than 80% based on pill returns). Use of Proc Mixed analyses allows all participants to be included if they contribute any data to the analysis dataset.

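### Section 12.2 gives its effect size of 0.25 no scale and leaves the target difference blank, so the 90% power claim for 35 completers cannot be reproduced for both outcomes from the printed inputs

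*Combined protocol and SAP*

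**What the plan says.** Section 12.2 says that the trial needs to "have at least 35 participants who complete the study" and gives the purpose as follows: "In order to ensure 90% power to detect an effect size of 0.25 for each outcome". The two-sided level is 0.025, called overall, in view of the primary and secondary endpoints. A parenthesis after the sample size gives an SD of differences of 5.8% "for EC insulin-signaling and 3.5% for flow-mediated dilation".

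The preceding paragraph of 12.2 reports prior-work values of −10 ± 9% for EC insulin response and 6.5 ± 4.3% for FMD. It then says: "An effect size of (how much) was used to calculate the expected sample size for the study". No target difference in percentage points appears anywhere in the document.

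The comparison being powered is described in two ways. Section 12.2 first speaks of each outcome "during the dapagliflozin treatment period compared to the placebo treatment period", and then of a repeated-measures analysis "to compare baseline and follow-up results for each treatment group". Section 4.2.2 says of FMD: "We will measure before and after each treatment period". Each person therefore contributes four measurements. Section 12.3 bases inference on a within-subject treatment effect: "A significant within-subject treatment effect is consistent with differences between the two treatments adjusting for carry-over and period effect".

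On attrition, 12.2 expects 42 randomized and 35 completing (83%), and puts non-completion at 7%.

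**The concern.** A sample size statement should let a reader recover the planned difference and check the power. Here 0.25 could be a standardized difference, Cohen's f or a relative change, and the sentence that should name the target is unfinished. The SD of differences could be that of the dapagliflozin-minus-placebo difference or of a baseline-to-follow-up change within one period. These choices alter the power at 35 completers several-fold.

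At stake are the checkability of the 90% claim and the interpretation of the result. A confidence interval will still be informative whatever the plan says. But a null finding cannot be set against a planned difference that was never stated. Read as a two-treatment difference on the scales tried below that use the printed SDs or means, 0.25 is compatible with, for example, 1.45 to 4.5 points for EC insulin response and 0.88 to 2.15 points for FMD.

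**Working it through.** **Inputs, all from 12.2:** n = 35 completers; two-sided alpha 0.025; SD of differences 5.8 (EC) and 3.5 (FMD); prior means −10 and 6.5; prior ± values 9 and 4.3.

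**Assumptions:** 0.025 applies to each outcome; the ± values are SDs; the test is a period-averaged within-subject treatment contrast; the printed SDs of differences are those of that contrast.

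**Formula:** noncentral t with noncentrality d·√n and n − 1 degrees of freedom, where d = difference ÷ SD of differences. Using n − 2 degrees of freedom changes these power figures by about 0.1 percentage point.

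**The plan's figure, by reading of 0.25:**

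| Reading | Difference EC / FMD (points) | d EC / FMD | Power at 35, EC / FMD | N for 90%, EC / FMD |
|---|---|---|---|---|
| 0.25 × SD of differences | 1.45 / 0.88 | 0.25 / 0.25 | 20.7% / 20.7% | 202 / 202 |
| 0.25 × single-measurement SD | 2.25 / 1.08 | 0.388 / 0.307 | 48.8% / 31.2% | 86 / 135 |
| 25% of the prior mean | 2.5 / 1.63 | 0.431 / 0.464 | 58.5% / 65.7% | 70 / 61 |
| Cohen's f on SD of differences (0.5 × SD) | 2.9 / 1.75 | 0.5 / 0.5 | 72.8% / 72.8% | 53 / 53 |
| Cohen's f on single-measurement SD (0.5 × SD) | 4.5 / 2.15 | 0.776 / 0.614 | 98.5% / 89.6% | 24 / 36 |

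For the first row, power is 0.8998 at n = 201 and 0.9014 at n = 202. The last row comes within rounding of 90% for FMD only. The table does not bound the possibilities: 0.25 percentage points would give 2.9% and 3.7%.

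**A repeated-measures ANOVA over the four measurements.** With f = 0.25, noncentrality is f²·N·4 ÷ (1 − ρ), on 3 and 3(N − 1) degrees of freedom. At ρ = 0.5 and N = 35 it is 0.0625 × 35 × 4 ÷ 0.5 = 17.5, and power is 90.6%; N = 34 gives 89.6%. This returns exactly 35, but ρ = 0.5 is not stated.

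If the SDs of differences refer to two single measurements, the printed values imply ρ = 1 − SD_diff² ÷ (2·SD²):
- EC: 1 − 33.64 ÷ 162 = 0.79, giving power above 99.9% at 35 and a minimum N of 16.
- FMD: 1 − 12.25 ÷ 36.98 = 0.67, giving power of 98.7% at 35 and a minimum N of 24.

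**What 35 completers can detect.** The d giving 90% power at n = 35 is 0.619. If the printed SDs are those of the dapagliflozin-minus-placebo difference, this is 0.619 × 5.8 = 3.6 points for EC and 0.619 × 3.5 = 2.2 points for FMD. If they are SDs of within-period change, multiply by √(2(1 − r)), where r is the correlation between a person's two changes:
- r = 0: 5.1 / 3.1 points
- r = 0.25: 4.4 / 2.7
- r = 0.5: 3.6 / 2.2
- r = 0.75: 2.5 / 1.5

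**Attrition.** 35 ÷ 42 = 83.3%, so 7 ÷ 42 = 16.7% do not complete. The printed percentages sum to 7 + 83 = 90. A loss of 7% would leave 42 × 0.93 = 39 completers.

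**The case against.** The strongest defence is that 35 can be recovered. The four-measurement ANOVA with f = 0.25 and correlation 0.5 returns exactly 35 for both outcomes, and 12.2 does speak of a repeated-measures analysis of data collected before and after each period. Cohen's f on the single-measurement SDs also comes close for FMD, which would then be the limiting outcome. On this view the defect is incomplete reporting, and the 21% figure is only one reviewer's reading, since the text never says that 0.25 is in units of the SDs beside it.

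Part of this stands. No single reading can be called the intended one, and a reader might infer from 21% and 202 that the trial is badly underpowered. The document does not support that inference, because it does not establish the scale on which those figures depend.

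The defence does not, however, rescue the power sentence. The ANOVA match needs a correlation that the plan does not state and that differs from those implied by its own SDs. It is also a 3-degree-of-freedom test across four measurements, not the treatment contrast that 12.3 uses for inference. The Cohen's f reading gives about 90% for one outcome only and uses a scale that the text never names.

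The placeholder may be leftover drafting, since the next paragraph supplies a number. That number still has no unit, so the gap remains.

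**Conclusion.** The concern holds as a failure of definition: the stated 90% power cannot be reproduced for both outcomes from the printed inputs. It depends on an effect-size scale, a test and possibly a correlation that 12.2 does not give. The illustrative power at 35 completers runs from about 21% to 98.5% within the table, but these are examples and not limits. They do not show that 35 is too few for the effect the sponsor had in mind.

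The figures rest on the assumptions listed in the working. If 0.025 were instead divided between the two outcomes (0.0125 each), 20.7% would become 13.9% and the 89.6% for FMD would become about 83%.

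The only plain arithmetic error is the 7% non-completion, which should be 17%. It leaves the planned 42 randomized and 35 completing unchanged.

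**What to change.** Leave the sample size unchanged while the original software input is recovered. Then revise 12.2 to state:

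1. the scale of the 0.25 and the test for which it was computed;
2. what the SD of differences is a difference of;
3. whether 0.025 applies to each outcome;
4. the sponsor's target difference in outcome units for each outcome, in place of the placeholder;
5. a power sentence that matches these inputs.

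If 5.8% and 3.5% are confirmed as SDs of the within-subject dapagliflozin-minus-placebo difference, and the tested term is the period-averaged treatment contrast, the power sentence should say that 35 completers give 90% power at two-sided alpha 0.025 for about 0.62 SD of differences (about 3.6 points for EC insulin response and 2.2 points for FMD). That is what 35 can detect and should not be presented as the planning target. If they are SDs of within-period change, state the assumed correlation between the two changes and recompute.

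Correct non-completion from 7% to 17% (7 of 42).

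The cost is retrieval of the input and rewording of 12.2, with no added participants, visits or procedures. The price is that the restated power or target difference may look less favourable than the present sentence.
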